Day 0: Subject presents fasting to the CHC. Blood pressure, heart rate, weight, height and waist circumference and body composition on InBody520 BioSpace will be recorded. FitBit® activity monitor placed. Subjects will have a jejunal feeding tube placed by the investigator using a CORPAK EAS™ and will then be randomized to the control or intervention group.

Day 0-Day 14: Subjects will take a mixed meal or electrolyte solution at a prescribed rate and interval and will be requested to eat ad lib only from provided meals of known caloric amount or from a list of low calorie items. Subjects will maintain a log of all food intake, temperature at least daily, tube position and symptoms and blood glucose 4 times a day.

Day 7: The subject will return to the CHC for review for continuation in the study, of their log and caloric intake and for adjustment of medication if necessary and activity monitor download.

Day 14: Day 0 measures will be repeated at the CHC and the tube removed. All uneaten food will be returned for caloric intake determination, activity monitor download.

Day 15-Day 28: The subject will maintain a medication and blood glucose log for 14 days after the removal of the tube.

Day 28: Exit outcome measures similar to those at Day 0.

Safety: The subjects will be monitored for fever, sore throat, displacement of the tube, gastrointestinal upset, vital signs, biochemical measures and weight change, and if pre-specified criteria are met or in the clinical judgment of the PI it is not appropriate to continue, will be withdrawn from the study.

Outcome Measures: weight change, caloric intake, waist and hip measurement, hormones and biochemical measures, physical activity, body composition, select symptoms, medication use, average self-monitored blood glucose level

Reimbursement: Subjects will receive standardized meals of known caloric amount for 2 weeks and up to \$300 cash.

Statistics This is a pilot study and sample size estimates are not appropriate. However based on studies of dietary restriction with a 1250 kcal diet for 1 week we anticipate identifying a significantly greater weight loss in the intervention arm with a sample size of 10 subjects/group. Fifteen subjects/group will be enrolled to allow for drop-outs.

Analysis: Primary analysis will be to compare change from baseline in outcome measures between the 2 groups using paired t-test. SC CTSI Biostatistics Department has aided in the study design.

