Subjects will have a 10 French 140cm tube placed using a CORPAK EAS™ by the PI or CoI following standard technique and will be randomized to the intervention or control group. (See Appendix A: Tube Placement Using EAS™). It usually takes about 20 minutes to place the tube but can take as little as 5 minutes or up to an hour. If the tube cannot be positioned in the intestine within 1 hour it may be allowed to move into position naturally overnight. In this case the participant would come back a day or 2 later to check that the tube has reached the correct position. In this case the tube feeds would only start when the tube is shown to be in the correct position.

Subjects will be provided with detailed instructions and logs for the following: (See Appendix B: Subject Packet).

1. Bolus nutrient administration and flushing of tube
2. Eating: to eat ad lib from provided meals of known caloric amount
3. Daily self-monitoring and tube care
4. 24 hour contact information
5. Need to monitor blood glucose prior to tube bolus
6. Use of FitBit activity monitor and daily activity

Prior to leaving, the subject will self-administer the first tube bolus and demonstrate by verbal response understanding of requirements for the study.

- Day 0-Day 14: (see Table 3)
- Intervention subjects will take mixed meal via jejunal tube at 10mls/min to satiety or to a maximum volume of 200mls 4 times a day. They will also take 200mls electrolyte solution 4 times daily orally.
- Control subjects will take electrolyte solution via jejunal tube at 10mls/min to satiety or to a maximum volume of 200mls 4 times a day. They will also take 200mls mixed meal solution 4 times daily orally.
- If for any reason the tube feed cannot be administered the remainder should be taken orally to ensure recommended daily intake of major nutrients and fluid is achieved.
- In addition all subjects will take the following daily: 2 10meq potassium chloride tablets, 2 600mg calcium tablets and 1 multivitamin tablet daily and 1/2tsp salt.
- In addition all subjects will be requested to eat ad lib from provided meals of known caloric amount.
- All subjects may also eat ad lib from very low or calorie “free” foods and drinks throughout the study from a provided list.
- Subjects will maintain a log of all food intake will check their daily temperature, tube position and symptoms and will contact the study team for specified symptoms or if they have any concerns they would like addressed.

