- As subjects adhering to very low-calorie diets usually have a fall in blood pressure, especially during the first week antihypertensive drugs will be discontinued unless moderate to severe hypertension is present.[33]

- Subjects will be requested to be as physically active as they like. Thus they are at liberty to increase, decrease or maintain their usual activity level.
- Similarly as most diabetic patients eating very low-calorie diets have marked improvement in hyperglycemia with blood glucose concentrations falling within the first one to two weeks oral hypoglycemic drugs will be discontinued for the first week of therapy. [33] An increase in activity level may also cause a fall in blood glucose levels. To aid in maintaining safe blood glucose levels subjects will be required to report to the study team if their blood glucose is over 250mg/dl on more than 2 consecutive measures or any value over 300mg/dl or less than 70mg/dl on any occasion. Symptoms of hypoglycemia (sweating, weakness, palpitations, confusion) will be reviewed with the participant at each visit. They will be advised to check their blood glucose if possible if such symptoms occur and to take one 15g glucose tablet (to be carried at all times) and repeat this every 15minutes until self-monitored blood glucose is over 80mg/dL or symptoms resolve.

Table 3 Summary of Nutrient Administration Days 0-Day 14

Item:	Intervention Group:	Control Group:
Ensure High Protein Shake (400kcal/800mls/100% protein RDA/day)	Via tube*	By mouth
Unflavored Pedialyte Electrolyte Solution (80kcal/800mls/~50% electrolytes/day)	By mouth**	Via tube*
Additional vitamins and electrolytes	By mouth	By mouth
Ad Lib food from that provided	By mouth	By mouth
Ad Lib “calorie-free” foods from provided list	By mouth	By mouth

*If unable to administer by tube the remainder to be taken by mouth

**Optional artificial flavoring (provided) may be added by subject if they wish to the orally ingested Pedialyte to increase palatability. This will be documented in the daily log.

Day 7: Subjects will return to the clinic for review of log and caloric intake. Medications will be triturated at the study clinician’s discretion in an attempt to attain euglycemia. The position of the tube tip will be assessed per FDA approved procedure by reinsertion of the subject’s own transmitting stylet and the tube will be repositioned if not located beyond the Ligament of Treitz.

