Day14: Baseline measures will be repeated. The position of the tube tip will be assessed per FDA approved procedure by reinsertion of the subject’s own transmitting stylet and then removed. All uneaten food will be returned for caloric intake determination, activity monitor download.

Day 15-Day 28: The subject will maintain a symptom and blood glucose log for 14 days after the removal of the tube.

Day 21: Subjects will return to the clinic for review of log and activity monitor. Medications will be titrated at the study clinician’s discretion in an attempt to attain euglycemia.

Day 28: Exit outcome measures similar to those at Baseline and Day 14.

Possible Additional Study Visits: Subjects will be seen at additional visits by the study team if they so request or if deemed appropriate by the study clinicians. Subjects will be encouraged to contact the study team if they do not feel well or if certain criteria are met. These specific criteria are:

- Self monitored blood glucose values over 200mg/dL on 3 scheduled checks
- Failure to ingest prescribed amounts of fluid
- Failure to administer tube feed on 2 successive occasions
- A morning oral temperature reading >37.2°C (98.9°F) or an afternoon temperature of >37.7°C (99.9°F)
- Pain that does not resolve spontaneously over 3 or 4 hours or with use of acetaminophen

Additional visits may be scheduled to determine position of the tube or to reposition the tip if it was not successfully placed in the jejunum at the initial visit or if the tube is blocked in which case attempts will be made to unblock it or it may be replaced.

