5.0 SELECTION AND WITHDRAWAL OF RESEARCH SUBJECTS

5.1 Inclusion Criteria:

- 18-70 years of age
- Type 2 diabetes on oral antidiabetic medication
- BMI ≥ 30 kg/m²
- A1C <9%

5.2 Exclusion Criteria:

- Use of any of the following medications: dipeptide-peptidase IV (DPP-IV) inhibitors (e.g., sitagliptin), GLP-1 analogs (e.g., exenatide) or medication that could alter glucose tolerance (e.g. steroids)
- Contraindication to tube (e.g. Prior upper gastrointestinal bleed, or history of easy bleeding, altered foregut anatomy due to obstruction or surgery)
- Known cardiovascular disease other than controlled hypertension.
- Pregnancy or unwilling to take contraception
- Active esophagitis
- Known hiatal hernia
- Active gastric ulcer and/or duodenal ulcers,
- Previous restrictive surgery of the gastrointestinal tract
- Crohn's disease
- Active cancer
- History of gastrointestinal hemorrhage

- Known upper gastrointestinal lesions with potential to bleed
- Use of NSAIDs or anticoagulants
- Psychiatric disorders other than mild depression
- Likely inability to adhere to study protocol including alcohol or drug dependent patients
- Type I diabetes,
- Liver, kidney or multi-organ dysfunction.
- Known eating disorders
- Inability to attend scheduled or unanticipated study visits
- Known prior abdominal problems or operations that could lead to adhesions or strictures and that could prevent the spontaneous passage of a 10 French jejunal tube if it were to dislodge distally.

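### Antihypertensives are withheld on a very low-calorie premise that ad lib food does not secure, with no stated end, home reading, blood-pressure limit or restart rule in the available text

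*Combined protocol and SAP*

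**What the plan says.** Section 5.2 excludes "Known cardiovascular disease other than controlled hypertension", so treated hypertensives whose pressure is controlled may enter. Under the Day 0 to Day 14 heading of section 3.0, the reason given for the stop is the fall in blood pressure on a very low-calorie diet, and "especially during the first week antihypertensive drugs will be discontinued unless moderate to severe hypertension is present". The rule applies to both arms.

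On diet, "all subjects will be requested to eat ad lib from provided meals of known caloric amount", on top of the shake and electrolyte solution. Table 4 in section 8.0 gives 480 kcal/day as a mandatory minimum. No maximum is given.

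On monitoring, subjects "will check their daily temperature, tube position and symptoms" and, per the Synopsis, measure glucose four times a day. Table 5 (section 9.0) schedules vital signs with a physician at Days 0, 7, 14, 21 and 28. The Synopsis provides a Day 7 visit "for adjustment of medication if necessary". Section 3.0 leaves titration at Days 7 and 21 to the study clinician's "discretion in an attempt to attain euglycemia". The Synopsis safety paragraph lists "vital signs, biochemical measures and weight change, and if pre-specified criteria are met", or if the principal investigator so judges, subjects are withdrawn.

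**The concern.** The protocol removes a protective treatment by rule and relies on the diet to replace its effect. If a subject eats well above the minimum, the expected fall may not come, and pressure may rise off drug. Such a rise may cause no symptoms, so a system that waits for the subject to report feeling unwell may miss it. What is at stake is subject safety in the first week of the hold and again when the provided diet ends at Day 14. The weight endpoint is not in question here.

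**Working it through.** **1. The plan's own calorie figure.** Section 4.1 gives the shake as 210 kcal per 14 fl oz and the electrolyte solution as 100 kcal per litre, 800 mL of each per day. Taking 29.57 mL per fl oz:

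- Shake: 210 / (14 × 29.57) × 800 = 406 kcal (stated as 400).
- Electrolyte solution: 100 × 0.8 = 80 kcal.
- Sum: 486 kcal/day, against the stated 480. The minimum reproduces.

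**2. Energy supplied above the minimum.** Appendix A, servings × kcal per serving: oatmeal 1,300; eggs 900; milk 1,800; tortillas 6,240; brown bread 1,320; white bread 1,650; soup 1,300; frozen entrées 2,800; non-frozen meals 2,800; canned meals 1,400; pudding 880; cookies 800; ice cream 1,440; canned fruit 560; apples 475; bananas 525; juice 1,680; vegetables 400. Total: 28,270 kcal.

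Appendix A does not say what period the list covers. Table 5 provides one week of food at Day 0 and again at Day 7.

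| Period covered by the list | Supplied food, kcal/day | With the 480 minimum |
|---|---|---|
| 14 days | 28,270 / 14 = 2,019 | 2,499 |
| 7 days | 28,270 / 7 = 4,039 | 4,519 |

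Section 1.0 describes a very low-calorie diet as 250 to 500 kcal/day. To stay at 500, a subject could eat only 20 kcal/day of the supplied food: 20 / 2,019 = 1.0%, or 20 / 4,039 = 0.5%. The Synopsis itself bases its expected weight loss on studies of a 1250 kcal diet. These are figures for supply, not intake. They show that the premise is not secured.

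**3. The two drug holds side by side.** Section 3.0 stops oral glucose-lowering drugs in the same list and by the same reasoning.

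| Feature | Glucose-lowering drugs | Antihypertensives (available text) |
|---|---|---|
| Duration | First week | Not stated |
| Home checks before Day 7 | 4 × 7 = 28 | 0 (no cuff in Appendix A Table E, no field in the Appendix C logs) |
| Contact limits | 70, 250 and 300 mg/dL, and "Self monitored blood glucose values over 200mg/dL on 3 scheduled checks" | None |
| Withdrawal limit (5.3) | Average daily glucose over 200 mg/dL on 2 or more days | None |
| Titration target at Days 7 and 21 | Euglycemia | None named |

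**4. The exception.** Moderate to severe hypertension has no mmHg value. The text does not say whether it means the underlying disease or the reading on treatment. For a subject controlled on drugs, that choice decides whether treatment stops.

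**5. Would a home limit work?** I simulated a limit of systolic 160 mmHg or above on 2 consecutive mornings. Assumptions, none from the documents: normal readings, day-to-day SD of 8 to 12 mmHg, serial correlation 0 or 0.5.

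- True mean 165, mornings 1 to 6: 86 to 94% detected.
- True mean 170, mornings 1 to 6: 95 to 99.6% detected.
- True mean 135, over 14 mornings: at most 3.3% trigger.
- True mean 145, over 14 mornings: 1.2 to 27.4% trigger.

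Most sustained rises would be found before Day 7. The price is some reviews of subjects with milder elevation.

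**The case against.** The case on the other side has substance.

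- **The stop is not universal, and its length is unclear.** A reader might infer that every treated subject is off drugs for 14 days. The text does not support that. There is an exception, and the 14 days comes only from the heading above the rule. The parallel glucose-drug hold lasts one week, and if this one does too, Day 7 is its end. The supportable defect is that the duration is not stated.
- **There is oversight.** A physician takes vital signs at each visit. Table 4 promises close endocrinologist monitoring with medication adjustment, and neither that nor the Synopsis Day 7 adjustment is limited to glucose. Extra visits are available, and the investigator may withdraw a subject. This stands, but all of it is discretionary, and before Day 7 it depends largely on the subject making contact.
- **The Synopsis does not promise a limit for every monitored item.** Sore throat has none in section 5.3 either, and investigator judgment is the named alternative. I therefore treat the missing vital-sign limit as a gap and not as a contradiction.
- **The population is selected.** Section 5.2 excludes other known cardiovascular disease and kidney dysfunction. That lowers the risk without removing it.
- **Part of the text is unseen.** Appendix B, which section 3.0 cites for daily self-monitoring, and the source cited for the hold are not available to me. Either could contain blood-pressure instructions.

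**Conclusion.** The concern holds in a limited form. The diet that justifies the hold is permitted but not secured in either arm. In the available text the exception is undefined, the hold has no stated end, no pressure is scheduled between Day 0 and Day 7, no blood-pressure limit triggers contact or withdrawal, and no restart is written. Followed as written, the rule can leave an eligible subject with controlled hypertension untreated and unmeasured for a week. This should be fixed, with medium confidence given the unseen text.

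Two further inferences go too far. The calorie supply does not show that blood pressure will fail to fall. Nor can the number affected be estimated: the documents do not say how many of the 30 enrolled take antihypertensives or how many would be exempt.

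**What to change.** All thresholds are defaults for the clinical team to confirm.

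- **Section 3.0, the hold:** state that the exception covers a history of moderate to severe hypertension even if now controlled on drugs, give the threshold, and state when the hold ends.
- **Appendix A Table E and Appendix C:** lend a home cuff to each subject whose drug is held, and add one morning blood-pressure row to the daily log.
- **Section 3.0, additional-visit criteria:** add contact for 160/100 mmHg or above on 2 consecutive mornings, any reading of 180/110 or above, or symptomatic low pressure. Contact prompts clinician review and, for high pressure, restart where indicated.
- **Section 3.0, Days 7, 14 and 21:** state that medication review covers blood pressure, with drugs restarted or titrated according to the measured off-drug reading. An automatic return to the full prior dose at Day 14 should be avoided. After two weeks of weight loss it could cause the low pressure that the hold was meant to prevent.

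The cost is at most 30 loaned cuffs (15 per group × 2), one log row, some unscheduled contacts and a few early restarts. No scheduled visits or subjects are added.

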5.3 Withdrawal Criteria

- Non-adherence to study instructions by subject for more than 2 days.
- Any request by subject
- Fever over 100.4 F, more than 1 episode of vomiting, gastrointestinal upset not relieved by reduction in tube feed, dislodged anchor or tube, average daily glucose over 200mg/dL on 2 or more days, weight change of >7% in first week of tube use.
- Clinical judgment of the PI (reason to be specified)

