Subjects may experience dumping symptoms of nausea, palpitations, sweating and abdominal pain during or for about 1 hour after jejunal nutrient infusion. The dose of the nutrient administered will be selected by the subject to achieve comfortable satiety. They will stop administering nutrient if they experience unpleasant symptoms. Symptoms, if they occur are usually mild and are transient and self-limited. We will exclude potential subjects from the study if they have any known cardiovascular disease (other than controlled hypertension) to minimize potential risks to the subject associated with possible palpitations in association with dumping syndrome.

Venipuncture

This study involves venipuncture of a peripheral vein. This is associated with a small risk of minor bleeding and infection at the puncture site. To minimize this risk, aseptic precautions will be used.

Risk of Hypoglycemia or Hyperglycemia

Alteration in diet and physical activity could lead to alterations in blood glucose: both hyperglycemia and hypoglycemia.

To minimize the risk of these complications the following precautions will be made:

- a. All participants will have the symptoms and signs of hyperglycemia and hypoglycemia reviewed with them as well as recommended management at each visit starting with the recruitment visit when the protocol is reviewed.
- b. As most diabetic patients eating very low-calorie diets have marked improvement in hyperglycemia with blood glucose concentrations falling within the first one to two weeks oral hypoglycemic drugs will be discontinued for the first week of therapy. [33] An increase in activity level may also cause a fall in blood glucose levels. To aid in maintaining safe blood glucose levels subjects will be required to report to the study team if their blood glucose is over 250mg/dl on more than 2 consecutive measures or any value is over 300mg/dl or less than 70mg/dl on any occasion.
- c. Information on managing hypoglycemia is provided in the FREE TO GO Study Instructions given to the participant.

Table 4 Summary of Steps Taken to Minimize Risk of Intervention

Concern	Precaution
Modified anchoring of orojejunal tube	Development by senior bioengineering and orthodontic specialists
Safety of orojejunal tube for 2 weeks	Potential risks reviewed with senior ENT and bariatric surgeon and deemed highly unlikely to occur Subjects will monitor their temperature and the tube position daily and report to the study team if any concerns

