Physical and psychosocial discomfort due to ambulatory use of orojejunal tube for 2 weeks	Intraoral anchoring makes tube inapparent to observers. They will be encouraged to take acetaminophen and take other steps to decrease discomfort of tube particularly in first few days of use. They will be shown how to remove the tube themselves at any time if they so desire
Back-up in event of distal tube displacement	Senior bariatric surgeon on study team
Safety of very low calorie diet for 2 weeks in subjects with type 2 diabetes	Close monitoring by specialist endocrinologist with adjustment of medication if needed. All subjects can take food and liquid ad lib. Mandatory minimum 480 kcal/d; 1.6litres fluid/day; 100% RDA high quality protein; 100% RDA electrolytes, minerals and vitamins.
Hyper- and Hypo-glycemia	Oral hypoglycemic drugs will be discontinued for the first week of therapy and participants will contact the study team if their glucose levels are less than 70mg/dL or over 250mg/dL. Participants will be educated on the symptoms of hypo- and hyper- glycemia and provided wth instruction and glucose tablets for the management of hypoglycemia.

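### The high-glucose contact rules disagree, and every required trigger lies above the withdrawal level; between 200 and 250 mg/dL contact is only encouraged

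*Combined protocol and SAP*

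**What the plan says.** The protocol gives three contact rules for high glucose and one withdrawal rule.

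- **Required report.** Section 3.0 (Day 0-Day 14) obliges subjects to report if "blood glucose is over 250mg/dl on more than 2 consecutive measures or any value over 300mg/dl or less than 70mg/dl on any occasion". Section 8.0, under the risk of hypo- and hyperglycemia, repeats the rule, ending "2 consecutive measures or any value is over 300mg/dl or less than 70mg/dl on any occasion".
- **Table 4 (Section 8.0).** "participants will contact the study team if their glucose levels are less than 70mg/dL or over 250mg/dL". It has no consecutive-reading condition and no separate 300 threshold.
- **Possible Additional Study Visits (Section 3.0).** "Subjects will be encouraged to contact the study team if they do not feel well or if certain criteria are met". One listed criterion is "Self monitored blood glucose values over 200mg/dL on 3 scheduled checks". It does not say whether the three checks must be consecutive, or over what period they count.
- **Withdrawal (Section 5.3).** "average daily glucose over 200mg/dL on 2 or more days".

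For context, Section 3.0 states that "oral hypoglycemic drugs will be discontinued for the first week of therapy". The synopsis has subjects log glucose four times a day. After tube placement the first scheduled review is Day 7: "Subjects will return to the clinic for review of log and caloric intake". The study calendar (Table 5) includes self-monitored glucose in that review. The tube-period log in Appendix C has a row for individual glucose values but none for the day's average.

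**The concern.** A rule for calling the team should act before, or at the latest together with, the rule for stopping. Here the required calls start above 250 mg/dL and the stopping rule starts at a daily mean above 200. They also conflict with one another: a single reading between 251 and 300 calls for contact under Table 4 but not under the Section 3.0 rule.

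What is at stake is safety alerting in a week when oral drugs are off and food is ad lib. Withdrawal depends on a daily average that no visible form asks anyone to calculate. If a subject at 200-250 does not act on the encouraged rule, the team may first learn at Day 7 that the withdrawal criterion was met days before.

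**Working it through.** **Inputs.** Four checks a day (synopsis). Contact and withdrawal rules as quoted above. The daily average is taken as the mean of the four scheduled checks, which is an assumption because Section 5.3 does not define it. Day 1 is taken as the first full day. No glucose distribution is assumed.

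**Step 1: examples over two days.**

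| Readings (mg/dL) | Daily means | Section 3.0/8.0 required | Table 4 | Encouraged (any 3 checks) | Withdrawal |
|---|---|---|---|---|---|
| 205 at all checks | 205, 205 | no | no | yes | met |
| 240 at all checks | 240, 240 | no | no | yes | met |
| 250 at all checks | 250, 250 | no | no | yes | met |
| 290, 290, 150, 290, then 150, 290, 290, 150 | 255, 220 | no | yes | yes | met |
| 260, 180, 180, 180 each day | 200, 200 | no | yes | no | not met |

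The fourth and fifth rows show the required rules disagreeing. The first three show withdrawal met with no required report.

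**Step 2: size of the gap.** The question is how high the daily mean can be on two consecutive days without any rule being met.

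- *Section 3.0/8.0 rule alone.* No value may exceed 300, and no three in a row may exceed 250. At most three of a day's four checks can then exceed 250, so the bound is (3 × 300 + 250)/4 = 1150/4 = 287.5. It is reached by 300, 300, 250, 300, then 300, 250, 300, 300.
- *Adding Table 4.* No value may exceed 250, so the bound is 250.
- *Also following the encouraged rule:*
  - Any three checks: at most two readings above 200 over both days, and each day needs one to have a mean above 200. Bound (3 × 200 + 250)/4 = 850/4 = 212.5.
  - Three checks in one day: at most two above 200 per day. Bound (2 × 200 + 2 × 250)/4 = 900/4 = 225.
  - Three consecutive checks: three of four at 250 is possible (250, 250, 200, 250, then 250, 200, 250, 250). Bound (3 × 250 + 200)/4 = 950/4 = 237.5.

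**Step 3: timing.** At a constant 240, the encouraged rule is met at the third check of Day 1 and withdrawal is met on Day 2. If the subject does not call, the next scheduled review is Day 7, and 7 − 2 = 5 days.

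**The case against.** The strongest reply is that 200-250 mg/dL is covered. The encouraged criterion is met in every constant profile in that band, and at 240 it is met the day before withdrawal can be. Even a required report relies on an ambulatory subject picking up the phone. This stands in large part: the gap is mainly the difference between encouraged and required. What remains is that the protocol uses mandatory wording where it wants a report, that the encouraged rule has no stated window, and that even its broadest reading leaves daily means just above 200 up to 212.5 uncovered.

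Second, Appendix B is not in the text reviewed. Section 3.0 describes a subject packet covering daily self-monitoring and round-the-clock contact, and it may contain a further rule. A reader might infer that subjects are never told to call at 200-250; the documents do not support that. Appendix B could not, however, remove the disagreement between Section 3.0 and Table 4.

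Third, Table 4 is a summary and may simply abbreviate the fuller rule. On that reading the conflict disappears, but the bound on the required rule rises from 250 to 287.5.

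Fourth, there are other safeguards: glucose values logged before tube placement are reviewed at Day 0, A1C must be below 9%, Table 4 promises close endocrinologist monitoring, and extra visits are allowed. Section 12.0 has staff completing the case report form daily, and they could average the four logged values. These lower the risk, but no daily contact with the subject is scheduled in the first week.

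**Conclusion.** The point holds as an inconsistency in safety alerting that is cheap to correct. The visible required high-glucose triggers disagree, and all lie above the withdrawal level. A subject with daily means above 200 and up to 250 can meet withdrawal with no required report before Day 7, up to about 5 days later. If the encouraged rule is followed as any three checks, the uncovered band is only daily means above 200 and up to 212.5. The figures assume that the daily average is the mean of four scheduled checks and that the visible text is the whole rule.

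Two stronger conclusions do not follow. The documents give no glucose distribution for these subjects off treatment, so the proportion who would pass through the gap cannot be estimated. Nor is there a basis for saying that the primary weight comparison is affected.

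A separate, minor inconsistency concerns insulin. The synopsis restricts entry to oral agents alone and excludes insulin; Section 5.1 lacks the restriction and Section 5.2 does not name insulin. Read alone, Section 5 could admit a subject on an oral agent plus insulin. The synopsis shows that this is not intended.

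**What to change.** State one required-report rule in the same words in Section 3.0 (including Possible Additional Study Visits), Section 8.0 and Table 4. The subject must contact the team for:

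- any value below 70 or above 250 mg/dL;
- values above 200 on any three scheduled checks within two days, not necessarily consecutive; or
- a mean of the day's available readings above 200.

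The first item covers the present 300 threshold and the consecutive-reading rule. The third closes the remaining band: 200, 200, 200, 250 on each of two days has only two readings above 200, but each day's mean is 212.5. Because withdrawal needs two days with a mean above 200, a call falls due at the first of them. Use the mean of available readings rather than a fixed total of 4 × 200 = 800, which fails if a check is missed: 250, 250, 110 totals only 610, but its mean is 610/3 = 203.3.

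Align the participant instructions with this rule. A log row for the daily mean would help but is optional.

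The cost is wording, a short daily calculation by the subject or staff, and some extra calls, whose number cannot be estimated from the documents. The two-day window means that three isolated readings above 200 spread over the fortnight would not force a call. That is narrower than the broadest reading of the present encouraged rule, but it keeps the burden reasonable.

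Separately, restrict Section 5.1 to oral antidiabetic medication only and list insulin in Section 5.2, to match the synopsis.
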